2.4.2 Prior and concomitant medications

Prior treatments are defined as treatments taken and stopped prior to the first dose of study treatment.

Any treatment given at least once between the day of first dose of randomized study treatment (Baseline) and 84 days after the last dose of study treatment or last visit (including follow-up visits) will be a concomitant treatment, including those which were started pre-Baseline and continued into the Treatment Phase.

Concomitant medications and prior medications taken within the 6 months preceding study enrollment will be captured at the Screening visit, and updated at Baseline, with ongoing or not ongoing information. Prior or concomitant medication will be identified based on recorded or imputed start and end dates of medication taken. Further rules are given in section 5.3.3.

Prior and concomitant treatments will be summarized by treatment arms in separate tables for the SAF and for the Treatment Phase and follow-up period, separately. Treatments will be presented in alphabetical order, by ATC codes and grouped by anatomical main group (the 1st level of the ATC codes). Tables will also show the overall number and percentage of subjects receiving at least one treatment of a particular ATC code and at least one treatment in a particular anatomical main group.

In addition, previous psoriasis therapy

- any “previous < biologic systemic /non-biologic systemic> therapy” (yes/no)
- previous biologic systemic therapy (yes/no, with embedded subgroup “Failure”* – yes/no),
- previous non biologic systemic therapy (yes/no, with embedded subgroup “Failure”* – yes/no),
- Previous topical (yes/no), previous phototherapy (yes/no), previous photochemotherapy (yes/no) and
- “Failure to at least 2 previous psoriasis therapy (biologic systemic, non-biologic systemic, topical, phototherapy and photochemotherapy)” (yes/no will also be summarized in a similar manner.

(* at least one therapy with lack of primary efficacy or lack of secondary efficacy or lack of tolerability).

In addition, medical procedures and significant non-drug therapies as coded in MedDRA will be summarized. “Surgical and Medical Procedures” eCRF page will be used to get this information. Concomitant Medications - Topical Corticosteroid will also be summarized similarly. Concomitant Medications - Topical Corticosteroid eCRF page will be used to get this information.

Previous psoriasis therapy will be available for chronic subjects only.

2.5 Analysis of the primary objective

The primary objective of this study is to demonstrate the superior efficacy of secukinumab 300 mg s.c. compared to nb-UVB in subjects with new-onset moderate to severe plaque psoriasis with respect to subjects achieving PASI 90 response at Week 52.

2.5.1 Primary variable

The primary efficacy variable is the proportion of subjects who achieve PASI 90 at Week 52. The analysis for the primary objective will be based on the FAS and mFAS.

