9.4.1 Primary variable

The primary efficacy variable is the proportion of patients who achieve PASI 90 at Week 52. The analysis for the primary objective will be based on the FAS.

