9.5.2 Investigator's global assessment mod 2011

The secondary efficacy variable is the proportion of all randomized patients who achieve at least IGA 0/1 response at Week 52. Patients will be considered responders if they achieve a score of 0/1 and improve by at least 2 points compared with baseline.

This analysis will be based on the FAS.

The method for IGA 0/1 response at Week 52 will use a logistic regression model similar to the primary analysis, with treatment as an explanatory variable and the significant variables among baseline IGA score, age, and body mass index, and their interactions with treatment. Forward selection procedure based on the likelihood ratio test would be used to select the best subset of covariates. The estimated adjusted odds ratio for Arm A1 versus Arm B1 will be displayed along with the associated 95% confidence interval.

If there were issues related to the convergence of the logistic regression model, the above hypothesis will be tested using a 1-sided Wald test.

Missing IGA 0/1 response values will be imputed with non-response regardless of the reason for the missing data (e.g., premature study discontinuation, missed visit, or administrative issue).

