2.6 Analysis of the key secondary objective

2.6.1 Key secondary variable

The key secondary variable is the proportion of all randomized subjects who achieve PASI 90 at Week 104. In order to reduce selection bias, all subjects who do not achieve PASI 90 at Week 52 will also be included in the analysis at Week 104 using the PASI improvement obtained at Week 104 only.

A subject who fails to achieve PASI 90 response at Week 104, irrespective of the responses over the past visits will be considered non-responder. Similarly, subjects who achieved PASI 90 response at Week 104, but not at any of the past visits will be considered responder.

This would mean that if a subject achieves PASI 85 (85% improvement in PASI score compared to Baseline) at Week 52, and the improvement in PASI increases to 90% at Week 104, the subject will be considered responder in the analysis at Week 104.

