2.6.2 Statistical hypothesis, model, and method of analysis

For the key secondary analysis, the following hypothesis testing will be performed:

$$H_{02}: p_{sec}^* = p_{nbUVB}^* \text{ versus } H_{A2}: p_{sec}^* > p_{nbUVB}^*$$

where p_{sec}^* and p_{nbUVB}^* are the proportion of subjects who achieve PASI 90 response at Week 104 in the secukinumab 300 mg s.c. (Arm A1) and nb-UVB (Arm B1) arms respectively. This testing will be performed using an exact logistic regression analysis similar to the primary analysis, with the strategy below under consideration. In case of no covariates is significant, exact logistic regression analysis will be performed using only Treatment as fixed effect factor.

Missing data will be handled similarly as for the primary endpoint analysis. Subjects who relapse will be considered non-responders in addition to those who discontinue the study before Week 104 because of lack of efficacy or AEs.

Testing strategy

Since the primary and the key secondary hypotheses are not mutually independent, an adjustment for multiplicity is considered here to control the alpha level (Type I error) i.e., familywise error rate.

This adjustment will be made using a hierarchical testing procedure which states that first H_{01} will be tested at 1-sided $\alpha=2.5\%$ level of significance. The obtained p-value from the fitted logistic regression model will be divided by 2 and this resultant p-value needs to be considered. If the resultant p-value is smaller than 0.025, H_{01} is rejected at 2.5% significance level, concluding that there is strong evidence to consider that secukinumab is performing better than nb-UVB at Week 52. However, if this resultant p-value is greater than 0.025, H_{01} is not rejected at 2.5% significance level, concluding that the evidence obtained from the observed sample is not strong enough to say that any one of the treatment arms is performing better than the other. "PASI score" eCRF page will be used to get above information.

The testing sequence will continue to test H_{02} at $\alpha=2.5\%$ (1-sided), only if H_{01} is rejected.

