2.7 Analysis of additional secondary objective(s)

2.7.1 IGA mod 2011 0 or 1 response

The secondary efficacy variable is the proportion of all randomized subjects who achieve at least IGA 0/1 response at Week 52. Subjects will be considered as **IGA mod 2011 0 or 1 responder** if they achieve a score of 0 or 1 and improve by at least 2 points on the IGA mod 2011 scale compared to Baseline.

IGA mod 2011 0 or 1 response at Week 52 will be analyzed using a logistic regression model similar to the primary analysis, with treatment as an explanatory variable and significant variables among Baseline IGA mod 2011 score, age, and BMI, and their interactions with treatment. Forward selection procedure based on the likelihood ratio test would be used to select the best subset of covariates. The estimated adjusted odds ratio for Arm A1 versus Arm B1 will be displayed along with the associated 95% confidence interval.

If there are issues related to the convergence of the logistic regression model, we will use a 1-sided Wald's test will be performed. This analysis will be based on the FAS and mFAS.

Time course plot for IGA mod 2011 0/1 response rates at scheduled visits upto Week 104 for imputed data and upto Week 208 based on observed data.

Handling of missing data

Missing IGA 0/1 response values will be imputed with non-response regardless of the reason for the missing data (e.g., premature study discontinuation, missed visit, or administrative issue).

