For the Mechanistic Sub-study, additional 12 randomized subjects will be treated for 104 weeks with secukinumab 300 mg s.c. (Arm A2), along with 12 subjects each from Arm A1b and Arm B1b, and will serve as active groups. Further, 12 subjects identified with chronic plaque psoriasis will be allocated to secukinumab 300 mg s.c. for 52 weeks (Arm C1) and another 12 subjects with chronic plaque psoriasis will be treated during 104 weeks with secukinumab 300 mg s.c. (Arm C2), both serving as control groups for the Mechanistic Sub-study. As the Mechanistic Sub-study will not involve any formal testing of hypothesis, the sample size for it is obtained in an illustrative manner.

4 Change to protocol specified analyses

In Study design section , under follow up subsection “PASI90 score” is mentioned in the protocol however it is updated as “PASI90 response”.

Randomized set is added.

[REDACTED]

PASI 75 is added in the section [2.13.2.1](#) and [2.14](#).

[REDACTED]

A new population called Modified full analysis set (mFAS) is introduced. Randomized subjects who received treatment are considered in this population. Primary, key secondary and additional secondary endpoints will be analysed using mFAS along with FAS. [REDACTED]

[REDACTED]

Statistical analysis for Week 156 will be performed at the actual scheduled visit Week 152.

5 Appendix

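### Does naming both the FAS and the mFAS for the tested endpoints leave it open which set decides H01 and H02?

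*SAP*

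**What the plan says.** Protocol 9.4.1 on the primary endpoint: "The analysis for the primary objective will be based on the FAS". Protocol 9.5.2 on IGA 0/1 at Week 52: "This analysis will be based on the FAS".

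SAP 2.5.1 widens the first to two sets, "The analysis for the primary objective will be based on the FAS and mFAS", and SAP 2.7.1 does the same for IGA: "This analysis will be based on the FAS and mFAS". SAP Section 4, the list of changes from the protocol, gives the origin: "A new population called Modified full analysis set (mFAS) is introduced". It continues: "Primary, key secondary and additional secondary endpoints will be analysed using mFAS along with FAS".

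SAP 2.2 defines the FAS as everyone randomised, under the intent-to-treat principle. The mFAS also requires at least one dose. Both analyse patients by assigned arm.

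SAP 2.6 names no analysis set, but SAP 2.6.1 fixes the denominator: "The key secondary variable is the proportion of all randomized subjects who achieve PASI 90 at Week 104". The gate in SAP 2.6.2 reads: "The obtained p-value from the fitted logistic regression model will be divided by 2 and this resultant p-value needs to be considered". H02 is tested only if H01 is rejected at one-sided 0.025.

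**The concern.** Two sets give two p-values for H01 and two for H02, while the gate speaks of one. Nothing in the SAP calls one set primary and the other supportive. The mFAS also appears among the changes from the protocol, so a reader could argue that the protocol's choice no longer settles the matter.

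The trial is open label. A patient who dislikes the allocated treatment may never start it, so a treated-only set need not preserve the randomised comparison. If the analyst could report whichever set crosses 0.025, the error rate for the gated tests would exceed its nominal level, and a borderline Week 104 result could be presented either way.

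**Working it through.** **Step 1: the plan's power (80 per arm, one-sided 0.025).** For H01 at 70% vs 28% (Protocol 9.8), the standard error is √(0.70×0.30/80 + 0.28×0.72/80) = √0.005145 = 0.0717. Power is Φ(0.42/0.0717 − 1.960) = Φ(3.90), above 99.99%; the plan states 99.9%. For H02 at 21% vs 4% (Protocol 9.9), exact enumeration of Fisher's test gives 90.0%; the plan states around 89%. The planning figures hold.

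**Step 2: which set the documents point to.**

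| Place | What it implies |
|---|---|
| Protocol 9.4.1 and 9.5.2 | FAS alone |
| SAP 2.1 | Analysis follows protocol Section 9 |
| SAP 2.2 | FAS is the intent-to-treat set |
| SAP 2.6.1 and 2.7.1 | Variables defined on all randomised patients, which the mFAS is not |
| SAP Section 4 | mFAS added beside the FAS |

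Section 4 also lists plain additions, such as the randomised set and PASI 75. Appearing there does not mean that the mFAS displaces the FAS.

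**Step 3: how untreated patients enter the FAS.** Protocol 6.1 classes patients who leave before the first dose as screening failures, so later PASI values are not expected. SAP 2.5.3 and 2.6.3 impose non-response for discontinuation through lack of efficacy or adverse events and, at Week 104, also for relapse or missing PASI 50 at Week 52. A never-treated patient would rarely fit these reasons. Other missing values are multiply imputed, separately by arm.

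**Step 4: expected gap in response rates.** The number untreated, u, is not given; I assume 2, 4 or 8 of 80, in one arm only. As a binary analogue of the planned imputation, draw each untreated patient's response from Beta(x+0.5, n−x+0.5), where x of n treated patients in that arm responded. The mean imputed rate is (x+0.5)/(n+1).

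- nb-UVB at Week 52, u = 8: x = 0.28×72 = 20.16. Imputed rate 20.66/73 = 28.3%. FAS rate (20.16 + 8×0.283)/80 = 28.03%, against 28% in the mFAS.
- nb-UVB at Week 104, u = 8: x = 0.04×72 = 2.88. Imputed rate 3.38/73 = 4.63%. FAS rate (2.88 + 8×0.0463)/80 = 4.06%, against 4%.

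Both gaps are under 0.1 percentage point.

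**Step 5: how often the decisions differ.** Simulation of the same analogue, with the log odds ratio (0.5 added per cell) pooled by Rubin's rules:

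| Untreated (secukinumab, nb-UVB) | H02 disagreement, 40,000 trials, 500 imputations | Repeat, 20,000 trials, 200 imputations |
|---|---|---|
| 0, 2 | 0.08% | 0.13% |
| 0, 4 | 0.03% | 0.15% |
| 0, 8 | 0.93% | 1.00% |
| 2, 0 | 0.02% | 0.03% |
| 4, 0 | 0.10% | 0.19% |
| 8, 0 | 0.02% | 0.06% |

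A further repeat reached about 1.2%. H01 disagreement was 0.00% throughout, apart from one trial in 20,000 in the repeat at (8, 0).

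**Step 6: error rate.** With equal true rates (28% or 49% for H01, 12.5% or 21% for H02) and 4 or 8 untreated, rejecting when either set rejects adds at most 0.0005 over the FAS alone (60,000 trials, 200 imputations). It adds at most 0.0009 in a repeat (40,000 trials, 100 imputations).

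**The case for a change.** The strongest opposing case has three parts.

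*A borderline result can flip.* If untreated patients count as failures in the FAS, 12/80 vs 4/80 gives a one-sided Fisher p of 0.031, while 12/76 vs 4/80 gives 0.024. Over whole trials at 21% vs 4%, the sets then disagree on H02 in 0.1–1.9%, 1.9–2.3% or 4.4–4.5% of trials with 2, 4 or 8 untreated in one arm. The arithmetic is right, but that missing-data rule is not the planned one for H01 or H02. Even under it, H01 power stays at 99.6% or more, so the gate almost always opens. The example also needs four untreated secukinumab patients, although the first dose is given on site at the randomisation visit. If the untreated are in the nb-UVB arm, every disagreement is a significant FAS and a non-significant mFAS, so the mFAS cannot rescue a failed FAS test.

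*Choosing between sets costs alpha.* Treating untreated patients as having their own observed responses gives an error rate of 0.030–0.033 for either set, against 0.026 for the FAS alone (Wald test, 28% in both arms, 2 to 8 untreated on nb-UVB). This needs responses that the trial is not expected to collect. Imputed values carry no new information about these patients, so the two tests nearly coincide.

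*For IGA, non-response is the planned rule.* This stands. At 80% vs 36% the mFAS difference is 44 points. With 2 or 8 untreated on secukinumab the FAS difference is 80×78/80 − 36 = 42.0 or 80×72/80 − 36 = 36.0. With the same numbers on nb-UVB it is 80 − 36×78/80 = 44.9 or 80 − 36×72/80 = 47.6. But IGA lies outside the gate, its variable is defined on all randomised patients, and both analyses are planned.

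It also stands that the SAP lacks an explicit ranking, and that the FAS text in SAP 2.2 does not mention the misrandomised patients whom Table 5-2 removes. The second is a clerical mismatch; the removal brings the two sets closer together.

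**Conclusion.** The observation about the text is correct, but it does not call for a change. The deciding set can be read from the documents as the FAS, and an analyst following the protocol would use it. Under an analogue of the planned imputation, with up to 8 of 80 assumed untreated in one arm, the sets agree on H01 in essentially every trial and on H02 in about 99% or more. Free choice between them would add at most about 0.001 to the error rate.

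A rewording would gain little. SAP 2.3.1 already plans counts of each analysis set by treatment and listings of disposition and set membership, so untreated patients will be visible. SAP 2.14.1 and 2.15 show that the Week 52 and Week 104 main-study analyses have been done, so new wording could not pre-specify those tests.

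The sizes rest on assumed untreated counts and on a binary, covariate-free Wald analogue. The SAP imputes PASI change under a normal model and then uses logistic regression at Week 52 and exact logistic regression at Week 104. A far larger untreated group in one arm, or many untreated patients recorded as leaving for adverse events or lack of efficacy, would weaken the conclusion on size but not the reading that the FAS decides.

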2.5.2 Statistical hypothesis, model, and method of analysis

For the primary analysis, the following hypothesis testing will be performed:

$$H_{01}: p_{sec} = p_{nbUVB} \text{ versus } H_{A1}: p_{sec} > p_{nbUVB}$$

where p_{sec} and p_{nbUVB} are the proportion of PASI 90 responders in the secukinumab 300 mg s.c. (Arm A1) and nb-UVB (Arm B1) groups, respectively.

The primary analysis method for PASI 90 response at Week 52 will use a logistic regression model with treatment as an explanatory variable and significant covariates among Baseline PASI score, age, and BMI. The best subset of the significant covariates will be selected using a forward selection method based on the likelihood ratio test. Interaction terms with treatment will also be considered, if significant, among the best subset of selected covariates and the treatment term.

Statistical significance will be evaluated at a 1-sided alpha level of 0.025. The estimated adjusted odds ratio for Arm A1 versus Arm B1 will be displayed along with the associated 2-sided 95% confidence interval (equivalent to the 1-sided 97.5% confidence interval) and p-value.

If there are issues related to the convergence of the logistic regression model, the above hypothesis will be tested using a 1- sided Wald test.

The primary analysis is not expected to be influenced by the use of topical treatment within the first 4 weeks since, any effect will be worn off by Week 52.

The detailed testing strategy including the primary endpoint analysis is provided in Section [2.6.2](#)

2.5.3 Handling of missing values/censoring/discontinuations

Missing data will be handled with a modified multiple imputation method. Subjects who discontinued the study before Week 52 because of lack of efficacy or AEs will be considered non-responders. Missing values for other reasons will be inserted by means of the multiple imputation method.

The multiple imputation method is a simulation-based approach where missing values are replaced by multiple Bayesian draws from the conditional distribution of missing data given the observed data and covariates (i.e., under the assumptions of missing at random (MAR)), creating multiple completed data sets, which can then be analyzed using standard methods. [Rubin \(1987\)](#) presented rules how to combine the multiple sets of estimates to produce overall estimates and confidence intervals that adequately incorporate missing data uncertainty.

Missing values for the “change from Baseline PASI score” will be imputed simultaneously based on an underlying normal distribution and using the data augmentation procedure of Markov Chain Monte Carlo (MCMC) method. The change from Baseline in PASI score appears to follow closer to a normal distribution than the actual PASI score. The imputations will be done separately for each treatment group (Arm A1 and Arm B1). For Arm A1 and B1, the imputation will also include Baseline PASI score, age, Baseline BMI as additional variable.

2.5.4 Supportive analyses

Sensitivity analysis will be performed on the primary analysis method for PASI 90 response at Week 52 by repeating the logistic regression model with treatment as an explanatory variable and all three covariates Baseline PASI score, age, and BMI. Interaction terms with treatment also will be considered.

If logistic regression model does not converge the following steps will be performed:

1. Run the PROC GENMOD procedure with EXACT statement;
2. If convergence not reached, remove the covariates from the model one by one until convergence is reached; start with continuous covariates (i.e., baseline BMI by replacing with BMI stratum (< 25, 25-< 30, >= 30), and then baselines PASI score), followed by removing categorical covariates (i.e., BMI stratum etc.);
3. If convergence not reached, perform 1 sided Wald test.

It should be noted that this model might not converge if response rates are too low.

The impact of missing data on the analysis results of PASI 90 at Week 52 will be assessed as well by repeating the logistic regression model using different ways to handle missing data.

- Non-responder imputation
- Tipping point analysis
- Last observation carry forward (LOCF)

A non-responder imputation will be used as a supportive analysis of the primary variable using logistic regression (forward selection method) as described in primary analysis method. In this analysis, a missing value of PASI 90 response at Week 52 will be imputed with non - response regardless of the reason for missing data (e.g., premature study discontinuation, missed visit, administrative issues).

Assuming significance is shown for the primary analysis using non-responder imputation, the tipping point analysis will investigate if, and at which point, significance is not achieved anymore as subjects imputed as non-responders are increasingly reclassified as responders independently for each treatment group.

For PASI 90 response, missing values will be replaced by LOCF. Baseline values will not be carried forward. Similar analysis will be performed using logistic regression (forward selection method) as described in primary analysis method.

An additional analysis might be considered including Week 52 assessments performed later than per visit windowing due to covid.

Scatter plot will be produced for study day analysis for Week 52 time window (Day 310 to 421) and PASI score stratified by pre pandemic and during pandemic phase. In Y axis PASI score and in X axis study day will be plotted.

For the figures with pre-pandemic and during pandemic phase, the definition is:

If the treatment period end date was before pandemic start, the pandemic phase is defined as “pre-pandemic”, otherwise defined as “during pandemic”. If a subject discontinued from treatment in treatment period and the discontinued date from study was before pandemic start, then the pandemic phase defined as “pre-pandemic”, otherwise defined as “during pandemic”. Pandemic start is defined as – 01MAR2020

Observed PASI score at Week 52 will be listed by pandemic phase (pre- and during-pandemic).

Descriptive analysis of absolute value of PASI scores (observed data) at Weeks 16, 24, 36, 52 up to Week 208 for all treatment arms will be provided. Descriptive analysis of absolute value of PASI score with MI method will be performed up to Week 104 only, where the missing PASI score will be imputed using multiple imputation. Graphical representation will be done using Dot plot and time course plot for PASI 90 response at week 52 and PASI score over time respectively. Percent change from baseline PASI score (multiple imputation) over time will be presented graphically for individual subjects through Spaghetti plots.

Follow-up phase visits where number of subjects in treatment group are very low it may give large imputed values and the covariance matrix in MCMC process can not be computed, hence, the analysis tables and graphs will be presented up to Week 104. Additionally, same analysis tables and graphs will be also repeated LOCF (for continuous endpoints) or NRI (for binary endpoints) . upto Week 104 Data beyond week 104 and upto Week 208 will only be summarized as observed data. All analysis will be performed using mFAS set.

A Separate Time course plot will be generated to display the Percentage (%) of patients with Total PASI absolute score < 3 with (NRI) approach upto Week 104.

For Mechanistic sub-study the summary statistics for PASI absolute score and change from baseline to post-baseline visits is summarized for FAS. Time course plot for percentage change from baseline PASI score and absolute PASI score will be provided for each treatment group separately. At time of Final analysis PASI score will be listed for FAS set.

